6.1.3 Unexpected Adverse Event

An adverse event not mentioned in the Investigator's Brochure or package insert or the specificity or severity of which is not consistent with the Investigator's brochure or package insert.

6.1.4 Determining Attribution to the Investigational Agent(s)

Attribution: An assessment of the relationship between the AE and the medical intervention. CTCAE does not define an AE as necessarily "*caused by a therapeutic intervention*". After naming and grading the event, the clinical investigator must assign an attribution to the AE using the following attribution categories:

Table 2 – Adverse event relationships

Relationship	Attribution	Description
Unrelated to investigational agent/intervention	Unrelated	The AE is clearly NOT related
	Unlikely	The AE is doubtfully related
Related to investigational agent/intervention	Possible	The AE may be related
	Probable	The AE is likely related
	Definite	The AE is clearly related

6.2 Adverse Event (AE) Reporting Requirements

Adverse events (AEs) will be recorded from the time of first study drug administration and for at least 30 days after treatment discontinuation, regardless of whether or not the event(s) are considered related to trial medications. All AEs considered related to trial medication will be followed until resolution, return to baseline, or deemed clinically insignificant, even if this occurs post-trial.

6.2.1 Reporting to the IRB

1. Unanticipated problems involving risks to subjects or others will be reported promptly to the IRB if they:

- were unexpected;

- were related or possibly related to the research; and
- suggests that the research places subjects or others at a greater risk of harm than was previously known or recognized.

If the adverse event does not meet all three (3) criteria listed above, the event does not have to be promptly reported to the Indiana University IRB. However, it should be reported at the time of continuing review.

2. Prompt reporting of adverse events to the IRB is defined as within 5 days for on-site studies and 5 days for offsite studies.

6.3 Data Safety Monitoring Board

A board to monitor safety of the intervention will be convened when 10 patients have been enrolled into the study, or at 3 months after the initiation of enrollment, whichever comes first. At the initial meeting, the DSMB will determine its meeting schedule for the remainder of the study. This board will consist of one intensive care physician, one pharmacist, one interventional neuroradiologist, and a statistician will be consulted to assist with data analysis. All adverse events will be reviewed by the board and summarized to be reported to the Indiana University IRB. The board will reserve the right to terminate the study based on quantity and severity of SAEs or if the data reveals there is no benefit.

7.0 Study Withdrawal/Discontinuation

Any participant or family member wishing to withdraw themselves from the study may alert the treating nurse, physician, or study coordinator at any time during their course. If a participant wishes to withdraw, this will be noted on the study database, no further information will be collected from that patient, however data collected up to that point may be used in final analysis. The investigators reserve the right to withdraw any patient if it is felt that further participation in the study will endanger the patients' health. If a patient is withdrawn by the investigator, the study team will still collect outcome data and all data collected may be used in final analysis. If a subject voluntarily withdraws from the study, they will be presented with the option to consent to continued data collection via a separate informed consent document. If they decline, no further data collection will occur.

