or anaphylaxis if allergic to the compound or an ingredient in the preparation. Any patients with low blood pressure will be treated with increased rates of intravenous (IV) fluids and vasoconstrictor agents to raise the blood pressure. This is standard of care for patients suffering from vasospasm already. At the discretion of the treating provider, any patients with dangerously low blood pressure, or other symptoms of shock, will have milrinone/placebo discontinued, however, their data will still be used in final analysis. Final outcome data will also still be collected on these patients.

Angiographic therapy may include:

- Diagnostic angiogram (using dye in the artery to look at blood flow in the brain)
- Use of medications injected into the arteries to dilate the arteries and relieve spasm
- Use of a balloon to dilate parts of the artery that are very tight.

The type of angiographic therapy that is used will be at the discretion of the treating provider. This is standard of care for patients with subarachnoid hemorrhage.

Women of childbearing age will receive a urine pregnancy test when they present to the hospital/emergency room as standard of care. This will occur prior to being approached by the research team.

6.0 Reporting of Adverse Events or Unanticipated Problems involving Risk to Participants or Others

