Appendix A – Data Points for Milrinone Protocol

➤ **Demographics**

- Name
- DOB
- Age
- MRN
- Study ID#
- Gender
- Ethnicity
- Race

➤ **Past Medical History**

- HTN
- Smoker

➤ **Presentation/Pre-Intervention Data**

- Date of SAH symptom onset
- Date of hospital admission
- Time of hospital admission
- Hunt/Hess score on admission
- Fischer score on admission
- Location of aneurysm (side and vessel)
- Size of aneurysm
- # of aneurysms
- Modality of treatment indicated (clip/coil/both)
- Date of treatment procedure
- Time of treatment procedure

➤ **Post-Intervention Data**

- First date of elevated TCD
- Time of first elevated TCD
- Measurement of first elevated TCD
- Severity of spasm
- Mean TCD throughout hospitalization
- Max TCD throughout hospitalization
- Need for EVD
- Date of clinical diagnosis of vasospasm
- Time of clinical diagnosis of vasospasm
- Duration of spasm
- Date of end of spasm
- Evidence of ischemic changes on CT prior to study drug initiation (date/time)
- Evidence of ischemic changes on CT any time during hospitalization (date/time)
- Vasopressor usage
 - Drug(s) used
 - Duration of use

➤ **Study Drug Data**

- Date study drug initiated
- Time study drug initiated
- Duration of study drug exposure
- Study drug dose at initiation
- Was study drug titrated up?

- Hemodynamic parameters
- Creatinine clearance checked during current admission prior to study drug initiation
- Was study drug discontinued early due to complications?

➤ **Angiographic Therapy Data**

- Results of angiogram
- Severity of spasm on angiogram
- Intra-arterial drug use?
- Number of times angiographic therapy required

➤ **Complications**

- Hypotension
- Tachycardia
- Arrhythmias
- Chest pain
- Others at discretions of provider

➤ **Outcomes**

- Length of ICU stay
- Date of transfer to floor
- Date of discharge
- Length of hospital stay
- Discharge disposition
- Modified Rankin Score at 6 months
- Modified Rankin Score at 12 months
- Whether patient received milrinone or placebo

Figure 1

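### Participant- or family-initiated withdrawal ends data collection unless a second consent is signed, and the adverse-event window in section 6.2 makes no matching exception

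*Combined protocol and SAP*

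**What the plan says.** Section 7.0 lets a participant or family member withdraw at any time by telling the nurse, physician or coordinator. From then on "no further information will be collected from that patient", although data already in hand may be analysed. Later in the same section, voluntary withdrawers get an offer: "they will be presented with the option to consent to continued data collection via a separate informed consent document". It continues: "If they decline, no further data collection will occur".

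Two other exits are handled differently:

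- **Investigator withdrawal (7.0).** "If a patient is withdrawn by the investigator, the study team will still collect outcome data".
- **Provider discontinuation (5.1).** Patients with dangerously low blood pressure or other symptoms of shock "will have milrinone/placebo discontinued, however, their data will still be used in final analysis". The protocol adds: "Final outcome data will also still be collected on these patients".

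Section 6.2 has adverse events recorded from the first dose and "for at least 30 days after treatment discontinuation, regardless of whether or not the event(s) are considered related to trial medications". Drug-related events are followed until they resolve, return to baseline or are judged clinically insignificant. Nothing in 6.2 mentions withdrawal. Section 6.1.2 makes any death within 28 days of the last dose a serious adverse event.

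**The concern.** Two decisions are merged when the request comes from the participant or family: to stop receiving the study drug, and to stop being followed. The same clinical event can therefore lead to different follow-up depending on who acts on it. If the provider stops the infusion for low blood pressure, the 6-month mRS is still collected. If the family asks to leave because of the same episode, or because of chest pain or headache, collection ends unless someone signs a new document.

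Three things are at stake:

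- **Primary outcome.** A 6-month mRS can be lost although nobody objected to a follow-up call.
- **Safety.** Adverse events after withdrawal, including deaths that 6.1.2 would count as serious, can go unrecorded. The board in section 6.3 may stop the study on the number and severity of serious events, so it relies on that record.
- **Comparability.** Section 5.1 lists hypotension, arrhythmias, tachycardia, chest pain and headache as risks of the drug. Requests to leave because of intolerance could be more frequent on milrinone, and the missing outcomes would then be related to arm.

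Section 8.0 gives no rule for a missing mRS and no allowance for attrition.

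**Working it through.** **1. The rules side by side**

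| Who ends it | Section | Outcome data afterwards | Adverse events under 6.2 |
|---|---|---|---|
| Treating provider (low blood pressure, shock) | 5.1 | Collected | At least 30 days |
| Investigator | 7.0 | Collected | At least 30 days |
| Participant or family, new consent signed | 7.0 | Collected | At least 30 days |
| Participant or family, new consent not signed | 7.0 | Not collected | 6.2 requires them; 7.0 forbids them |

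Only the last row loses data, and only there do 6.2 and 7.0 give opposite instructions. No section describes a participant or family ending study treatment while staying in follow-up under the original consent. Appendix A asks "Was study drug discontinued early due to complications" but lists no item for the type or reason of a withdrawal.

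**2. The plan's sample size (section 8.0)**

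Inputs: 50% vs 75% with mRS of 2 or less, two-sided 5%, 80% power, chi-square test. Pooled proportion = 0.625.

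n per arm = [1.960 × √(2 × 0.625 × 0.375) + 0.842 × √(0.5 × 0.5 + 0.75 × 0.25)]² / 0.25²
= [1.960 × 0.6847 + 0.842 × 0.6614]² / 0.0625
= 57.7, so 58. The plan states 59, which is reproduced within rounding.

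Power at n = 59 is Φ[(0.25 × √59 − 1.3419) / 0.6614] = Φ(0.874) = 0.809.

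**3. What losses would do**

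The documents give no withdrawal rate, so every loss below is an assumption.

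One lost mRS: 1/59 = 1.7 percentage points of an arm.

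Power with the same loss in both arms, taking losses as unrelated to outcome:

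| Loss per arm | Evaluable per arm | Power |
|---|---|---|
| 2% | 57.8 | 0.801 |
| 5% | 56.0 | 0.788 |
| 10% | 53.1 | 0.766 |
| 20% | 47.2 | 0.715 |

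With loss in one arm only, power is 0.798 at 5%, 0.786 at 10% and 0.758 at 20%.

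Best-to-worst range of the treatment difference, with all 59 kept in each denominator:

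- 5 lost on milrinone and 1 on placebo: 5/59 + 1/59 = 8.5 + 1.7 = 10.2 points.
- 2 lost and 1 lost: 2/59 + 1/59 = 5.1 points.

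Bias if losses are related to outcome, with no true effect (50% in both arms) and a fraction w lost on milrinone only, of whom a fraction g would have done well: observed milrinone rate = (0.5 − w × g) / (1 − w).

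- w = 0.10, g = 0: 0.5 / 0.9 = 55.6%, or +5.6 points.
- w = 0.10, g = 0.25: 0.475 / 0.9 = 52.8%, or +2.8 points.

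**The case against.** The best defence is that section 7.0, read whole, is one coherent rule: a person withdraws, is asked about follow-up, and collection stops if they say no. The offer goes to every voluntary withdrawer, and accepting it has nearly the effect sought here. The event that prompted the request is already recorded, because 6.2 starts at the first dose and earlier data may be used. The 30-day window can be read as a general rule that the specific withdrawal rule limits, which would make the conflict a missing cross-reference. The protocol also gives little reason to expect much intolerance: section 1.0 reports no complications in 88 patients treated elsewhere, and providers and patients are blinded.

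Much of this stands, and it rules out several stronger readings that a reader might infer:

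- *Voluntary withdrawal always ends data collection.* It does not. Those who sign the second consent are still followed.
- *Drug-related withdrawals in general lose safety data and the primary outcome.* They do not. Provider stops for low blood pressure or shock and investigator withdrawals keep outcome data.
- *Participants are never offered a way to end treatment only.* The consent pages are not available for this review, so the options in the original consent cannot be judged. The protocol text describes no such route, and that is all that can be said.

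Two things survive. Continued collection still needs a fresh signature rather than resting on the original consent. Eligibility requires a new focal deficit or a change in mental status (3.1), and a representative may have to consent, in person (4.0), so a signature may not always be obtained even where nobody objects to follow-up. And since 6.2 states no exception, site staff have two written instructions that cannot both be followed.

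**Conclusion.** The point holds in limited form. It is a stated rule that, followed as written, can lose 6-month mRS values and late adverse events. The loss affects only participants who withdraw, or are withdrawn by family, and for whom no second consent is signed. For those who do so inside the adverse-event window, 6.2 and 7.0 contradict each other.

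The size is unknown. The sample size has almost no reserve: about 2% loss in both arms uses up the margin above 80% power, and 10% brings power to 0.77. These figures assume that losses are unrelated to outcome. A reader might take the 10.2-point range as an expected bias against the 25-point target, but the documents do not support that. It is an outer bound on assumed counts, reached only if every lost patient in one arm goes one way and every lost patient in the other arm goes the opposite way. Whether withdrawals would be more frequent on milrinone is plausible from the listed risks but is not shown. The change is still worth making, because it is cheap and an outcome not collected may not be recoverable.

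**What to change.** Limit the change to data collection; it should set no rule on when the infusion is stopped.

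- In 7.0, and in the consent if it does not already do so, distinguish (a) ending study treatment from (b) refusing further data collection.
- In case (a), continue adverse-event recording per 6.2 and mRS at 6 and 12 months under the original consent, with no second consent.
- End collection only in case (b), on explicit refusal, and replace the present default accordingly.
- State in 6.2 that only such refusal overrides the 30-day rule.
- Add to Appendix A which case applied, the date and the reason.

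The cost is revised wording submitted to the IRB and a few more follow-up contacts. No procedures are added, and participants keep the right to refuse all follow-up.

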8.0 Statistical Considerations

Sample size justification: Literature on the natural history and outcomes specifically of patients who suffer DIND is sparse. Based on our own experience, we expect to see mRS of 2 or less in approximately 50% of patients in the control group. With a sample size of 59 patients per group, the study will have 80% power to detect a 25% difference between the experimental and control groups (75% vs. 50% with mRS of 2 or less), assuming a two-sided chi-square test conducted at a 5% significance level.

The experimental and control groups will be compared for differences in baseline demographics and clinical characteristics using chi-square tests for categorical variables and Wilcoxon Rank Sum tests for ordinal and continuous variables. The primary outcome, mRS 2 or less at 6 months, will be compared between groups using chi-square tests. Secondary outcomes, including need for angiographic therapy, mRS 2 or less at 12 months, presence of side effects/complications, and discharge disposition will be compared between groups using chi-square tests, and mRS scores at 6 and 12 months, duration of vasospasm, and hospital and ICU lengths of stay will be compared between groups using Wilcoxon Rank Sum tests.

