3.1 Inclusion/Exclusion Criteria

Inclusion

- Subjects \geq 18 years of age
- Aneurysmal subarachnoid hemorrhage, proven on CT angiogram or digital subtraction angiography
- Aneurysm treated, either by endovascular embolization or surgical clip ligation
- Evidence of increased velocities on transcranial dopplers (TCDs) and/or radiographic evidence of vasospasm as seen on angiogram
- Cerebral vasospasm as demonstrated by patient's clinical exam (new focal deficit or change in mental status not attributable to any other cause)

Exclusion

- Recurrent subarachnoid hemorrhage
- Untreated ruptured aneurysm, for any reason
- Patients who die prior to treatment for aneurysm
- Patients who are not able to complete at least 6 months of follow-up
- Patients who are admitted already in vasospasm (i.e. a delayed admission)
- Creatinine clearance less than 20 ml/min
- Women with a positive pregnancy test or who are lactating
- Other comorbidity which may adversely affect patient outcome, at the discretion of the principal investigator

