4.0 Enrollment/Randomization

Location: IU Health Methodist Hospital, [name]

Process: Patients diagnosed with aneurysmal subarachnoid hemorrhage will be identified at the time of diagnosis and the research team will be contacted by the admitting team to monitor the patient. The patients will be consented and enrolled into the study as soon as possible following surgery or endovascular intervention, if the PI (or his assigned designee) determines the patient to meet all criteria other than evidence of vasospasm. A subject ID number, which is arbitrary, will be assigned to the patient once consented so that patient confidentiality may be protected. They will not, however, be randomized at this point. The patient's Legally Authorized Representative (LAR) will be contacted for consent if the patient is unable to provide it. If a LAR is not present at the bedside, initial contact may take place over the phone to establish a time to discuss the study and obtain consent in person. At the time of diagnosis of clinical vasospasm, the treating physician(s) will notify the research team. At this time, eligibility will again be reviewed with the PI (or his assigned designee) and the protocol orders will be signed and scanned to the pharmacy where they will be entered into CERNER and the pharmacy will randomize the patient to standard hyperdynamic therapy with placebo (normal saline) or standard therapy + milrinone. Randomization will take place at the time of protocol entry into CERNER. The diagnosis will be at the judgment of the treating physician and confirmed by the PI (or his assigned designee). Providers and patients will remain blinded to the drug. An index of which patients received the drug will be maintained by pharmacy services.

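### The primary test leaves out age and admission Hunt/Hess grade; prespecified adjustment is a cheap gain whose size the documents cannot settle

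*Combined protocol and SAP*

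**What the plan says.** Section 8.0 (Statistical Considerations) sizes the trial and analyses it with the same test. The design rests on the statement that "we expect to see mRS of 2 or less in approximately 50% of patients in the control group". With 59 per group, "the study will have 80% power to detect a 25% difference between the experimental and control groups" (75% against 50%), "assuming a two-sided chi-square test conducted at a 5% significance level". The analysis sentence is: "The primary outcome, mRS 2 or less at 6 months, will be compared between groups using chi-square tests". No adjusted or stratified analysis is described.

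The same section plans baseline testing: "The experimental and control groups will be compared for differences in baseline demographics and clinical characteristics". It does not say what follows if a difference is found.

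Section 4.0 (Enrollment/Randomization) says that "the pharmacy will randomize the patient to standard hyperdynamic therapy with placebo (normal saline) or standard therapy + milrinone". This happens when the protocol orders are entered, after clinical vasospasm has been diagnosed, and no stratification factor is named. Appendix A lists age and "Hunt/Hess score on admission" among the data to be collected. Both are therefore fixed before allocation.

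**The concern.** Covariates fixed before randomisation can be adjusted for without bias from treatment. If they predict 6-month mRS, adjustment removes outcome variation that the chi-square leaves in the error term. The data are already being collected, so the gain costs no patients.

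Two features make this worth raising. First, the design has little slack: power is just above 80%, no inflation for loss is stated, and the target difference is 25 points. Second, baseline tests are planned with no rule for using them. If grade or age turns out imbalanced, someone must choose between an adjusted and an unadjusted result after seeing data, and that choice can decide the conclusion.

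**Working it through.** **1. The plan's own figure.** Inputs from Section 8.0: control 50%, experimental 75%, two-sided 5%, power 80%. With pooled variance, the mean rate is 0.625 and

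n = [1.96·√(2·0.625·0.375) + 0.842·√(0.25 + 0.1875)]² / 0.25² = 57.7, so 58 per arm.

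The stated 59 agrees within one patient. Exact enumeration of the uncorrected chi-square gives power of 80.87% at 59 per arm. Exact size is 5.28%, 4.89% and 5.21% at common success rates of 50%, 62.5% and 75%. The planned test is sound and matches the sample size.

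**2. Gain from adjustment.** The documents give no prognostic strength, so every input in this step beyond the design rates is an assumption.
- Hunt/Hess grades 1 to 5 at 15/25/30/20/10%, and age normal with SD 1 (full spread).
- Narrowed spread: grades 2 to 4 at 30/50/20%, and age SD 0.7.
- Intercepts set so that marginal success stays at 50% and 75%.
- 40,000 trials per scenario; the SE of each paired power difference is 0.08 to 0.17 points.

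The adjusted test is the Wald test of treatment in a logistic model with grade and age as linear terms.

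| Scenario | Log-odds per grade / per age unit | Control success, grade 1 to 5 | Chi-square to adjusted power (%) | Change (points) |
|---|---|---|---|---|
| None | 0 / 0 | 50% throughout | 81.05 to 80.89 | -0.2 |
| Very weak | 0.15 / 0.10 | 57% to 42% | 80.82 to 80.98 | +0.2 |
| Weak | 0.30 / 0.20 | 63% to 35% | 80.72 to 81.90 | +1.2 |
| Moderate | 0.50 / 0.35 | 71% to 26% | 80.52 to 83.83 | +3.3 |
| Strong | 0.80 / 0.50 | 80% to 16% | 80.79 to 87.67 | +6.9 |
| Narrowed, weak | 0.30 / 0.20 | – | 81.18 to 81.55 | +0.4 |
| Narrowed, moderate | 0.50 / 0.35 | – | 81.11 to 82.43 | +1.3 |
| Narrowed, strong | 0.80 / 0.50 | – | 81.11 to 84.09 | +3.0 |
| U-shaped grade effect | – | – | 80.70 to 80.47 | -0.2 |

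With no prognosis and grade coded as five categories, adjusted power is 80.66%, a loss of 0.4 points.

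**3. In patients.** Exact chi-square power is 81.8% at 60 per arm, 84.3% at 63, 87.6% at 71 and 88.0% at 72. Adding each gain to 80.87% gives:
- Full spread: about 1 (weak), 4 (moderate) or 12 to 13 (strong) extra patients per arm.
- Narrowed spread: under 1, about 1 to 2, or about 3 to 4.

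**4. Cross-check.** If the covariates explain a share R² of within-arm outcome variance, the effective size is 59/(1 - R²). Assumed R² of 0.05, 0.10, 0.20 and 0.30 gives power of 82.9%, 84.9%, 88.8% and 92.5%. Simulation with a single prognostic score agreed. The weak, moderate and strong gains above correspond to modest R²: 1 - 59/60 = 0.02, 1 - 59/63 = 0.06, and 1 - 59/71 to 1 - 59/72 = 0.17 to 0.18.

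**5. Type I error.** The adjusted Wald test rejected in 4.8% to 5.2% of null trials, and in 4.9% to 5.2% with mean filling of missing grade.

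**6. Missing grade** (assumed rates, completely at random). Change in power, in points, against the chi-square on all patients:

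| Missing, handling | None | Weak | Moderate |
|---|---|---|---|
| 5%, dropped | -2.2 | -1.0 | +1.5 |
| 5%, overall mean filled in | -0.2 | +1.1 | +3.1 |
| 10%, dropped | -4.6 | -3.3 | -0.7 |
| 10%, overall mean filled in | -0.2 | +1.0 | +3.1 |

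**7. A smaller true effect.** At an assumed 70% versus 50% (20,000 trials each), power went from 60.0% to 59.6% (none), 60.3% to 61.7% (weak), 60.7% to 64.3% (moderate) and 60.6% to 68.8% (strong).

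**8. How often the choice matters.** At 75% versus 50%, the adjusted and unadjusted tests disagreed on significance in about 5% (weak), 7% (moderate) and 10% (strong) of simulated trials.

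**The case against.** The strongest reply is that nothing is wrong. The chi-square is valid, prespecified and matched to the sample size, so replacing it is a preference. That the plan contains no error is true and is accepted here.

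The gain also depends on chosen inputs. The full-spread scenarios put 10% of patients in grade 5, but Section 3.1 requires vasospasm to be evident on clinical examination, which may make the worst-grade patients harder to qualify. It also excludes patients with "Other comorbidity which may adversely affect patient outcome, at the discretion of the principal investigator". Grade is scored at admission, before vasospasm develops. These points stand: the narrowed figures may be nearer the truth.

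The small downside holds only at full enrolment. At an illustrative 20 per arm, power with no prognosis fell from 37.4% to 35.3%, and the model diverged in 0.3% to 0.6% of trials. Section 6.3 does allow early termination. However, Section 10.0 plans to enrol to the powered size, and no divergence was seen at 59 per arm. What remains is that a fallback should be named.

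Finally, the Wald test concerns a conditional odds ratio while the reported effect is a risk difference, and missing covariates matter only because the model needs them. Both are real complications, and both can be settled in the text: the test and the interval disagreed in only 0.1% to 0.6% of simulated trials, and mean filling removes nearly all the loss from missing grade.

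**Conclusion.** The concern holds as an efficiency point, with medium confidence in its practical value. The plan's test is valid and its 59 per group reproduces. At full enrolment, adjustment for grade and age would plausibly change power by between -0.2 and +6.9 points, and by no more than about +3 if eligibility narrows their spread. When the covariates do not help, the cost is about 0.2 to 0.4 points. These figures rest on assumed prognostic strength, grade mix and spread, and should not be quoted as properties of this trial. The case for acting is the asymmetry between a small loss and a possibly useful gain, together with the value of naming one deciding test before any imbalance is seen.

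**What to change.** Before unblinding, amend Section 8.0 to state:

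- **Primary analysis:** logistic regression of mRS 2 or less at 6 months on treatment, admission Hunt/Hess grade (linear) and age (linear). The two-sided 5% Wald test of treatment decides, whatever the baseline comparisons show.
- **Missing covariates:** fill with the overall mean across both arms, using neither treatment nor outcome, so that no patient with an outcome is dropped.
- **Effect measure:** a standardised risk difference with 95% CI, which stays on the 75% versus 50% scale. Name the variance method, for example robust variance multiplied by 118/114 with a t reference on 114 degrees of freedom. In simulation this gave coverage of 94.7% to 95.1% and a mean half-width of 17.2 points (no prognosis) to 15.5 (strong). State that the interval is descriptive if it and the Wald test disagree.
- **Sensitivity analysis:** the unadjusted chi-square, which could also be named as the fallback if the model fails to converge.

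Keep to two covariates. Expected poor outcomes are 59 × 0.50 + 59 × 0.25 = 44, or about 15 for each of the three model terms.

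The cost is one paragraph. No new data are needed and 59 per arm stands. The price is reliance on a prespecified model and the small loss of power if grade and age do not help. That loss grows if grade is coded as five categories without need or if incomplete patients are dropped.

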2.0 Rationale and Specific Aims

The goal of this study is to assess the efficacy of milrinone as an agent to treat cerebral vasospasm by adding it to standard therapy. This will take the form of a randomized, controlled trial in which patients will receive either standard hyperdynamic therapy or hyperdynamic therapy + milrinone. The primary outcome of interest will be modified Rankin Scale (mRS) at 6 months (+/- 60 days). Secondary outcomes assessed will be need for angiographic therapy, mRS at 12 months (+/- 60 days), duration of vasospasm (in days), hospital and ICU lengths of stay, side effects/complications of both modalities of therapy, milrinone dose, name and dose of drug(s) used for intra-arterial injection, number of times angiographic therapy is required, vasopressor usage, and discharge disposition.

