6.1.1 Adverse Event (AE)

An adverse event is defined as any unintended or abnormal clinical observation that is not of benefit to the patient. Either the condition was not present prior to study intervention, or it has worsened in intensity or frequency following study intervention. Adverse events will be graded according to the NCI Common Toxicity Criteria, Version 4.0 and will be logged for all patients in both arms of the study. The following grading scale will be used:

0 = No adverse event or within normal limits

1 = Mild adverse event

2 = Moderate adverse event

3 = Severe and undesirable adverse event

4 = Life-threatening or disabling adverse event

5 = Death related to adverse event

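### The only planned safety comparison is one pooled, undefined yes/no outcome, which can dilute an excess of a named milrinone risk; compare the named events separately

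*Combined protocol and SAP*

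**What the plan says.** Section 2.0 names as a secondary outcome "side effects/complications of both modalities of therapy", without dividing it into event types. Section 8.0 turns this into a presence-or-absence outcome: "presence of side effects/complications, and discharge disposition will be compared between groups using chi-square tests". It gives no event list, grade cut-off, attribution rule or time window.

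Two other places could supply the definition, and 8.0 cites neither:

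- **The adverse event log (6.1.1 and 6.2).** An adverse event is "any unintended or abnormal clinical observation that is not of benefit to the patient", if new or worsened after the intervention. Events are "graded according to the NCI Common Toxicity Criteria, Version 4.0 and will be logged for all patients in both arms of the study". They are "recorded from the time of first study drug administration and for at least 30 days after treatment discontinuation", and no judged link to the drug is required.
- **The complications list (Appendix A).** It has fields for hypotension, tachycardia, arrhythmias and chest pain, followed by "Others at discretions of provider".

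Section 5.1 names the infusion risks as hypotension, arrhythmias, tachycardia, chest pain and headache. It also says that the top titration dose is above the currently approved maximum for heart failure.

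**The concern.** A yes/no score over a pooled set of events gives a patient with a drug-related event the same value as a patient with an unrelated one. The more often unrelated events occur, the fewer patients are left whose score the drug can change, and the smaller the difference between arms becomes. Both candidate sources have this property: the log because it takes almost anything, the Appendix A list because it combines four events and an open category.

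The matter is worth settling because the trial is randomised and placebo-controlled, whereas the only safety figure the protocol offers is an uncontrolled series with no complications in 88 patients (section 1.0). Section 8.0 plans no other between-arm analysis of harm. If its one test is insensitive, a non-significant result may be read as evidence of safety that it cannot give. Since the outcome is undefined, two analysts could also obtain different safety results from the same data.

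**Working it through.** **1. The plan's own figure.** Inputs from 8.0: 50% vs 75%, two-sided 5%, 80% power, chi-square test. Without continuity correction,

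n = [1.96·√(2·0.625·0.375) + 0.842·√(0.50·0.50 + 0.75·0.25)]² / 0.25² = 57.7, so 58 per group.

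Power at 59 per group is 80.9%. The stated 59 is therefore reproduced, and the uncorrected chi-square test is used below.

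**2. One named risk tested alone.** Assume hypotension in 10% vs 30%, at 59 per arm. Adding the probabilities of all 59-vs-59 tables that are significant at 5% gives power of 80% (0.805). The normal approximation gives 78%.

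**3. The same excess inside a pooled yes/no.** Let b be the proportion with any other event, equal in both arms and independent of hypotension. Then

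any-event rate = 1 − (1 − b)(1 − hypotension rate).

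For b = 50%: control 1 − 0.5·0.9 = 55%; milrinone 1 − 0.5·0.7 = 65%. A 20-point excess becomes 10 points.

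| Background b | Control | Milrinone | Difference | Power, 59 per arm |
|---|---|---|---|---|
| none (tested alone) | 10% | 30% | 20 points | 80% |
| 20% | 28% | 44% | 16 points | 44% |
| 50% | 55% | 65% | 10 points | 20% |
| 80% | 82% | 86% | 4 points | 9% |
| 90% | 91% | 93% | 2 points | 7% |

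**4. What the test can show when the control rate is high.** With 53/59 controls (90%) scoring yes, only 59/59 on milrinone is significant (p = 0.012). With 56/59 controls (95%) scoring yes, even 59/59 is not (p = 0.08).

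**5. The recording window, if 8.0 were to use it.** The window in 6.2 is anchored to the end of infusion, and 5.1 makes infusion length depend on symptoms. For creatinine clearance above 50 mL/min, the weaning limit in 5.1 (0.75 mCg/kg/min over 72 hours) gives these minimum times:

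- Not titrated up: 72 h symptom-free + 72 h weaning = 6 days.
- Titrated up: 24 h + 72 h + 120 h weaning (1.25/0.75 × 72 h) = 9 days.

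Adding 30 days gives minimum windows of 36 and 39 days. Under a constant hazard, an event rate of 50% over 39 days becomes 1 − 0.5^(36/39) = 47% over 36 days. In an extreme case, with one whole arm stopped at day 1 and the other infused for 14 days, the windows are 31 and 44 days, and 50% becomes 1 − 0.5^(31/44) = 39%.

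**The case against.** **Section 8.0 could mean the short list, or one test per complication.** The first is possible, and nothing in the plan excludes it. The short list still pools four events with an open category, and a background of only 20% nearly halves the power. The second is weakly supported. The plural for the chi-square tests settles nothing, since 8.0 uses it for the single primary outcome too.

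**The event rates are invented.** They are assumptions, as is independence. The model also lets the drug change only one component. If milrinone raised several pooled events together, the loss would be smaller. The direction of the dilution from unrelated events does not depend on the exact rates, but its size does.

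**Safety is protected elsewhere.** Events are graded and logged in both arms, attribution is assigned (6.1.4), and the monitoring board reviews all events and may stop the study (6.3). That protects patients during the trial. It does not define the final comparison in 8.0.

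**Two stronger readings that a reader might infer.** One is that nearly every patient in both arms will score yes. The documents give no event rate for these patients. The 0 of 88 counts complications attributed to milrinone in an uncontrolled series and decides nothing either way. Nor does any section tie the outcome in 8.0 to the definition in 6.1.1.

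The other is that the response-dependent window tilts the comparison toward milrinone. Section 8.0 does not adopt the 6.2 window, and the 30 days there is a minimum, not an end. The typical shift is about 3 points at a 50% rate. A patient whose infusion is stopped for shock has already scored yes, so a shorter window cannot change that patient's result. If nearly everyone did score yes, the window would matter even less.

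**Conclusion.** The point holds as a defect of definition and sensitivity in one secondary outcome. Section 8.0 specifies a single pooled presence-or-absence comparison without saying what it contains, and each available source mixes the named drug risks with other events. For an assumed 10% vs 30% excess of hypotension at 59 per arm, pooling lowers power from 80% to between 44% and 7% for independent backgrounds between 20% and 90%. A non-significant result from such a test should not be taken as reassurance.

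The documents do not establish a ceiling or a material window bias. The window is a minor refinement. The primary outcome and the sample size are unaffected.

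**What to change.** In 8.0, replace the pooled outcome with separate between-arm comparisons of:

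- hypotension, tachycardia, arrhythmias and chest pain, each of which has its own field in Appendix A;
- headache, which 5.1 names as a risk and Appendix A omits, taken from the adverse event log.

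Report each as a risk difference with a 95% confidence interval, state any grade cut-off and attribution rule, and list all other events descriptively by arm. For the assumed 10% vs 30%, the interval would be about 20 ± 14 points (1.96·√[(0.10·0.90 + 0.30·0.70)/59] = 0.14), which tells the reader far more than one pooled p-value.

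As a refinement, count events in one common period, for example 30 days from first dose. The recording in 6.2 already covers this for every dosed patient, except after death or after voluntary withdrawal with refusal of further collection (7.0). A patient randomised but never dosed has no start date under 6.2, so 8.0 should say how such a patient is handled. The recording rule in 6.2 can stay as it is.

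The cost is a change of wording in 8.0 and a few small tables, with no new data collection and no change in sample size. The downside is several safety comparisons instead of one, which should be read as descriptive, and events after the common period would be listed and not tested.
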